2 SCHEDULE OF EVENTS

Table 1: Schedule of Events

Trial Period:	Screening Phase	Radiotherapy	Treatment Cycles		Safety Follow-up	Follow-up ¹⁷	Progression (Upon first progression)
Treatment Cycle/Title:	Screening	SABR±CRT ³	Day 1 Cycle 1	Day 1 Cycle 2-8			
Scheduling Window (Days):	-35 to -1	Commence within 4 weeks of registration ³	5 days post SABR ± 3 days	21 days post previous cycle Day 1 ± 3 days	30 days from date of last dose of pembrolizumab ± 3 days	3 months from SABR ± 14 days	
Clinical/Administrative Assessments							
Informed Consent	X						
Inclusion/Exclusion Criteria	X						
Demographics and Medical History	X						
Disease Specific Medical History	X						
SINS score for Spinal Targets	X						
Full Physical Examination	X		X	X			
Directed physical Examination						X	
Vital Signs ¹ and Body Measurements	X		X	X		X	
ECOG Performance Status	X		X	X		X	
Review Adverse Events ²	X		X	X	X	X	X
Radiotherapy planning	X						
Trial Treatment Administration – SABR ³		X					
Trial Treatment Administration – Pembrolizumab ⁴			X	X			See section 10.6
Review Prior/Concomitant Medications	X		X	X			
Numerical Pain Rating Score		X	X	X		X	
New Anti-Cancer Therapy Status / Second phase pembrolizumab					X	X	X
Survival Status ¹⁸						X	
Laboratory Procedures/Assessments: analysis performed by LOCAL laboratory							

Trial Period:	Screening Phase	Radiotherapy	Treatment Cycles		Safety Follow-up	Follow-up ¹⁷	Progression (Upon first progression)
Treatment Cycle/Title:	Screening	SABR±CRT ³	Day 1 Cycle 1	Day 1 Cycle 2-8			
Scheduling Window (Days):	-35 to -1	Commence within 4 weeks of registration ³	5 days post SABR ± 3 days	21 days post previous cycle Day 1 ± 3 days	30 days from date of last dose of pembrolizumab ± 3 days	3 months from SABR ± 14 days	
Pregnancy Test ⁵ – Urine or Serum β-HCG	X		X	X			
Haematology ⁶	X		X	X		As clinically indicated	
Chemistry ^{7,8}	X		X	X			
T3, FT4 and TSH ⁹	X		X	X			
PT/INR and aPTT ¹⁰	X						
HIV, Hepatitis B and C ¹¹	X						
Tumour Evaluation							
Tumour assessment by CT scan or MRI ¹² (Chest, Abdo, Pelvis) reported as per RECIST 1.1	X				X (Every 3 months from SABR)		
CT scan (Brain) (if clinically indicated) ¹²	X			X (Cycle 4 & 8 only)		As clinically indicated	
Whole body bone scan (if clinically indicated) ¹²	X			X (Cycle 4 & 8 only)		As clinically indicated	
Metastatic FFPE Biopsy ¹³	X					X (month 9 only)	X
Primary Surgery FFPE sample ¹⁴	X						
Blood Serum Sample		X	X	X		X (9, 12 and 24 months)	X
Whole Blood Sample ^{15,16}		X	X	X		X (9, 12 and 24 months)	X

Clinical/Administrative Assessments

- Vital signs include blood pressure, heart rate, respiratory rate and temperature. Height will be measured at screening only.
- Baseline abnormalities (using CTCAE v4.03) must be recorded from signature of informed consent to prior to start of treatment. Adverse events (using CTCAE v4.03) are then required to be assessed on day 1 of every pembrolizumab cycle and at 30 days following last pembrolizumab treatment. SABR related adverse events will be collected at every subsequent follow-up visit until 2 years after completion of SABR.

3. Conventional hypofractionated radiotherapy of **30-36Gy** may be delivered to individual lesion(s) if SABR is determined to be not technically or safely possible to deliver. If CRT is required it must be completed prior to SABR administration. **At least one lesion must receive SABR.**

4. Pembrolizumab should be administered at 5 days (+/- 3 days) of the last SABR treatment for a total of 8 cycles.

Laboratory Procedures/Assessments – All diagnostic laboratory tests should be performed within 10 days of study registration (to determine eligibility), and also within 3 days prior to every cycle of pembrolizumab (unless indicated otherwise below)

5. Urine or serum pregnancy test for patient of childbearing potential should be performed within 7 days of study registration and also 72 hours within first dose of pembrolizumab. If the urine test is positive or cannot be confirmed as negative, a serum pregnancy test will be required.

6. Haematology: Haematocrit, haemoglobin, platelet count, white blood cell count (total and differential), red blood cell count, absolute neutrophil count and absolute lymphocyte count.

7. Chemistry: Carbon dioxide (if considered standard of care only), uric acid, calcium chloride, glucose, phosphorus, potassium, sodium, magnesium, total protein.

8. Liver Function Tests: Albumin, Alkaline Phosphatase (ALP), Alanine Aminotransferase (ALT), Aspartate Aminotransferase (AST), Lactate Dehydrogenase (LDH), Gamma-Glutamyl Transferase (GGT, total bilirubin and direct bilirubin if total bilirubin is elevated above the ULN), Kidney Function Tests: Urea, creatinine.

9. Thyroid Function: T3, T4 and TSH.

10. Coagulation Profile: PT (INR), aPTT. These need only be done if there is clinical concern regarding patient anticoagulation.

11. HIV, Hepatitis B and C tests only need to for those patients at risk of prior or current active infection as determined by the investigating clinician. These tests only need to be performed within 7 days of study registration only.

Tumour evaluation - Screening CT and WBBS should be completed within 35 days prior to study registration.

12. Clinical and radiological tumour assessments will be performed by CT scan (or MRI as required if tumour is in extremity) at screening and every 3 monthly post-SABR treatment until the last evaluable patient completes 12 months of follow-up.

Brain CT will be performed if clinically indicated at the same time points. Whole body bone scans will be performed at 3 and 6 months post SABR treatment only in patients with bone disease at baseline and as clinically indicated at the 3 monthly post SABR treatment follow-up visits.

Disease progression should be confirmed with repeat imaging 4 to 6 weeks later by the same imaging modality or by biopsy. If PET-CT scan has been done clinically this can be used for confirmation of disease progression provided the CT component of the PET-CT scan is of adequate resolution.

Biological Evaluations

13. If an archival biopsy specimen from a metastases exists then this should be submitted (block or unstained slides). An optional biopsy of metastatic site will be performed at 9 months post completion of SABR, if feasible. This will ideally be the same site as biopsied before trial related treatments (also optional). In event of disease progression - A sample from the metastatic site, if feasible, is requested. If taken, one-two formalin-fixed, paraffin-embedded (FFPE) tumour blocks should be requested.

14. If the patient had surgery for the primary tumour, one tumour block from resection should be submitted.

15. Prior to radiotherapy, first dose of pembrolizumab (all cycles), at disease progression (if this occurs) and at 9, 12 and 24 months post SABR treatment, whole blood samples will be collected for immune endpoints (refer to the RAPPORT Laboratory Manual for details on collection and processing).

16. EDTA whole blood sample (refer to the RAPPORT Laboratory Manual for details for collection and processing).

Follow-Up Visits

17. Study Follow-Up Visits - follow-up assessments (e.g visits @ 1, 3, 6, 9, 12, 15, 18, 21 and 24 months post end of SABR Treatment) should be undertaken within \pm 14 days of the scheduled time point. In the event of overlapping visits (i.e. between day 1 of each pembrolizumab cycle and post-SABR follow-up visits), only one visit is required but all protocol mandated investigations (for both timepoints) must be undertaken.

18. All patients will be followed for survival until the last evaluable patient completes 12 months of follow-up. Participants who start a new systemic therapy, are retreated with pembrolizumab or who have distant progression will be followed for survival only.

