3 TRIAL SUMMARY

Title	Stereotactic R adiotherapy and A nti- P D1 antibody (P embrolizumab) for O ligometastatic R enal T umours
Abbreviated Title	RAPPOR
Trial Phase	Phase 1b/II
Clinical Indication	Patients with oligometastatic renal cancer (1-5 metastases) considered safe for stereotactic ablative body radiosurgery (SABR)
Trial Type	Prospective, single arm study
Route of administration	SABR treatment (18Gy-20Gy/1#) followed by 200mg pembrolizumab (MK-3475) IV once every 3 weeks for a total of 8 cycles (~6 months).
Trial Blinding	Open label
Number of trial subjects	30 evaluable* patients in total.
Estimated enrolment period	24 months
Estimated duration of trial	36 months
Duration of Participation	~20 months

* Evaluable patients are defined as participants who complete at least one SABR treatment and receive at least one dose of study drug (18-20Gy/1# to at least one lesion with at least one dose of pembrolizumab).

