10.1.14 Tumour Imaging and Assessment of Disease

Imaging will be performed as per below:

- All pre-registration/screening investigations (CT Scan and WBBS) should be completed within 35 days prior to study registration.
- Clinical and radiological tumour assessments (post study registration) will be performed by CT scan or MRI (Chest, Abdo, Pelvis, and Brain if clinically indicated) reported with RECIST 1.1 (if possible) unless evidence of progression earlier or clinically inappropriate. WBBS will be performed at 3 and 6 months post SABR treatment in patients with bone disease detected at baseline, and/or if clinically indicated at any of the 3 monthly follow-up visits. Follow-up visits will continue until the last evaluable patient completes 12 months of follow-up.

Disease progression, as per RECIST 1.1, should be confirmed with repeat imaging 4 to 6 weeks later by the same imaging modality or by biopsy. If PET-CT scan has been done this can be used for confirmation of disease progression provided the CT component of the PET-CT scan is of adequate resolution. Complete response includes disappearance of the target tumor radiographically or metabolically (standardized uptake value = 0 when the pre-treatment PET, if done, was metabolically active). Efficacy will be evaluated by time to local progression as well as failures in other sites.

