10.8.1 Adverse Event Reporting

All adverse events will be recorded from the time the consent form is signed through 30 days following completion of pembrolizumab treatment. SABR related adverse events will be followed at each follow-up visit until 2 years after completion of SABR.

All adverse events, which occur whilst the participant is enrolled on the trial (including the follow-up phase), must be reported in the patients' medical records and recorded on the Adverse Events CRF. The Common Terminology Criteria for Adverse Events (CTCAE version 4.03 – see appendices) or other more specific AE tools must be used to grade the severity of an event. Laboratory values need reporting as AEs only if abnormal and deemed clinically significant by the investigator

All adverse events must be recorded on the Adverse Events CRF with the following information:

- The severity grade using CTCAE version 4.03
- Its relationship to the study drug(s)
- Treatment changes
- Whether it constitutes a serious adverse event (SAE)

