10.8.2 Late Toxicities

Late toxicities (AEs) which are deemed by the investigator to be attributed to protocol specified SABR treatment are to be reported on the AE CRF. Late Toxicities are defined as AEs directly attributed by the Investigator to SABR treatment on this study, recorded from 30 days post last MK-3475 treatment until 24 months following the last SABR treatment.

10.8.3 Definition of an Overdose for This Protocol and Reporting of Overdose to the Sponsor and to Merck

For purposes of this trial, an overdose of pembrolizumab will be defined as any dose of 1,000 mg or greater (≥ 5 times the indicated dose). No specific information is available on the treatment of overdose of pembrolizumab. Appropriate supportive treatment should be provided if clinically indicated. In the event of overdose, the participant should be observed closely for signs of toxicity. Appropriate supportive treatment should be provided if clinically indicated.

If an adverse event(s) is associated with ("results from") the overdose of pembrolizumab, the adverse event(s) is reported as a serious adverse event, even if no other seriousness criteria are met.

If a dose of pembrolizumab meeting the protocol definition of overdose is taken without any associated clinical symptoms or abnormal laboratory results, the overdose is reported as a non-serious Event of Clinical Interest (ECI), using the terminology "accidental or intentional overdose without adverse effect" on the Adverse Event CRF page.

All reports of overdose with and without an adverse event must be reported within 24 hours to the Sponsor and within 2 working days hours to Merck Global Safety. (Attn: Worldwide Product Safety; [contact]).

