11.2.9 Sample Size Calculation

This is a Phase Ib/II study to evaluate the safety profile and efficacy that would then be evaluated in a larger and more appropriately powered future study. The sample size of 30 patients is pragmatic.

The primary objective of the study is to provide a description of the safety profile of the combined SABR and pembrolizumab therapies. Table 8 illustrates different scenarios for grade 3 or 4 AEs rate ranging from 0% to 40% with the respective 95% exact confidence intervals, assuming 30 patients.

Table 8: Confidence Intervals for Adverse Event Rates

Number of patients with grade 3+ AE	Grade 3+ AE rate	95% confidence interval
1	3%	0% - 17%
2	7%	1% - 22%
3	10%	2% - 27%
4	13%	4% - 31%
5	17%	6% - 35%
6	20%	8% - 39%
7	23%	10% - 42%
8	27%	12% - 46%
9	30%	15% - 49%
10	33%	17% - 53%
11	37%	20% - 56%
12	40%	23% - 59%

Expected toxicities related to the pembrolizumab treatment are listed in the Investigator's Brochure. Therefore, immune related events such as hypothyroidism, pneumonitis, and colitis are expected. They should occur in <5%. Pneumonitis and colitis are considered to be the most serious but are rare events. Immune events and other events of clinical interest will be monitored for closely in this study, with early stopping rules as detailed below.

Recruitment will occur over a two-year period. An interim analysis after 15 patients completes 6 months of follow-up will be conducted for presentation purpose. The final analyses will be at the completion of 12 months after the last participant has completed SABR treatment.

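### SABR toxicity is to be collected to 24 months, but visits and the only final report close 12 months after the last patient, so later entrants cannot complete the late-toxicity window

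*Combined protocol and SAP*

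**What the plan says.** **Collection window.** Footnote 2 of the Schedule of Events states that "SABR related adverse events will be collected at every subsequent follow-up visit until 2 years after completion of SABR". Section 10.8.1 repeats it: "SABR related adverse events will be followed at each follow-up visit until 2 years after completion of SABR". Section 10.8.2 defines late toxicities as SABR-attributed events "recorded from 30 days post last MK-3475 treatment until 24 months following the last SABR treatment". Footnote 17 gives the visit grid as an example: "e.g visits @ 1, 3, 6, 9, 12, 15, 18, 21 and 24 months post end of SABR Treatment". None of these limits the window by date of entry.

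**Closure.** Section 10.1.14 says: "Follow-up visits will continue until the last evaluable patient completes 12 months of follow-up". Footnote 12 and section 10.4 end imaging at the same point, and footnote 18 and section 10.5 end survival follow-up there. On analysis, section 11.2.9 says: "The final analyses will be at the completion of 12 months after the last participant has completed SABR treatment". Section 13.5 plans two reports, the second and final one 12 months after the last participant's SABR.

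**Calendar.** The Trial Summary estimates 24 months of enrolment and 36 months in total. Its "Duration of Participation" row gives about 20 months.

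**Analysis.** Section 7.14 makes safety, both acute and long term, the primary endpoint. Section 11.2.3 plans the maximum grade of each event and the proportion of patients with grade 3 or higher toxicity, with an exact 95% CI. It sets no time horizon and does not separate acute from late events.

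**The concern.** A patient treated late in accrual has a 24-month toxicity window on paper, but visits stop well before it ends. No passage says that toxicity review continues past closure, and none says that the window is shortened for later entrants.

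This bears on the primary endpoint. Under the planned estimator, a patient watched for 12 months and one watched for 24 carry equal weight, and the unwatched months of the first count as free of events. The long-term part of the safety result may then be too low, and nothing in section 11.2.3 would tell a reader how many patients were under review late in the window. Section 7.10 itself names relatively short follow-up as a limitation of earlier SABR studies.

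**Working it through.** **Inputs.** 30 evaluable patients, 24 months of enrolment and 36 months in total (Trial Summary); closure 12 months after the last patient (10.1.14); window to 24 months after SABR (footnote 2, 10.8.1, 10.8.2); first pembrolizumab dose 5 days after SABR, eight cycles 21 days apart (Schedule of Events). The accrual pattern is not stated, so even accrual is an assumption and is varied in step 5. Entry is treated as the date of SABR.

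1. **The plan's own duration.** 24 + 12 = 36 months, which reproduces the stated figure. Full windows for all patients would need 24 + 24 = 48 months.

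2. **Who can finish.** A patient treated at month t has 36 − t months of potential follow-up. Reaching 24 months requires t ≤ 12. With 30 evenly spaced entries from month 0 to month 24, 15 qualify and 15 do not (14 do not if the month-24 visit may be 14 days early). Mean follow-up capped at 24 months is 20.9 months.

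3. **Length of the late window.** It opens at day 5 + 7 × 21 + 30 = 182, or about 6.0 months after SABR with no dose delays. It therefore lasts about 18.02 months. The last patient is observed for 12 − 6 = 6 of those 18 months.

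4. **Late patient-time.** Planned: 30 × 18.02 = 541 patient-months. Delivered under the spacing in step 2: 448, or 83%. About 17% is lost.

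5. **Sensitivity to accrual shape.** Let cumulative accrual be G(t) = (t/24)^k. The share unable to finish is 1 − (12/24)^k. The mean loss per patient is 12 − 24 × (1 − 0.5^(k+1))/(k+1) months, and dividing by 18.02 gives the share of late time lost.

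| Accrual | Cannot reach 24 months | Late time lost |
|---|---|---|
| k = 0.5 (front-loaded) | 29% (about 9 patients) | 1.66/18.02 = 9% |
| k = 1 (even) | 50% (15) | 3.00/18.02 = 17% |
| k = 2 (back-loaded) | 75% (22 to 23) | 5.00/18.02 = 28% |

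6. **Sensitivity to accrual length.** With even accrual over R months and closure 12 months later, the share unable to finish is 12/R: 67% for R = 18, 40% for R = 30, 33% for R = 36.

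7. **Exits to survival-only follow-up.** Footnote 18 and section 10.4 move patients with distant progression, new systemic therapy or retreatment to survival-only follow-up. The documents do not say whether SABR toxicity is still collected in them. If it stops, and a share s leaves before 24 months independently of entry date, the number incomplete under even accrual is 30 × (1 − 0.5 × (1 − s)). Assumed values of s = 20%, 40% and 60% give 18, 21 and 24 of 30.

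**The case against.** The strongest reply is that the rules can be read together. Footnote 2 and 10.8.1 tie toxicity collection to follow-up visits, so 24 months may be only a cap: early entrants stop there, and later entrants stop when visits stop. That is ordinary administrative closure. The grid in footnote 17 is only an example, and the 36 months is an estimate. Alternatively, the closing sentence sits in the imaging section, and 10.8.2 gives toxicity its own patient-level end. A reader might infer a flat contradiction, but the cap reading makes that too strong. It does not remove the problem, because the plan never states the cap or handles the unequal follow-up. If collection did continue past closure, no planned report would contain the later data.

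Other stronger readings also fail:

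- **A promised 2-year safety claim.** No passage plans one. Section 11.2.3 has no horizon, and section 7.14 gives long-term events a start but no end.
- **Demonstrated under-counting.** Section 7.10 names late risks such as fracture and renal impairment without timing. The individual serious events that the background does time fell within a year: 10 weeks and 4 months (7.7.3), and 10 months (7.6). Section 10.8.5 also keeps treatment-related serious events reportable at any time once they come to the investigator's attention. That is a passive route and does not replace scheduled review, but it limits the loss for serious events. Under-counting is a risk of unknown size.
- **The 20-month participation figure as proof.** It is consistent with the truncated mean of 20.9 months, but the plan does not say how it was derived.

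It is also fair that the trial is descriptive with a pragmatic sample size, and that the early stopping rule, judged at 12 weeks, is unaffected.

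**Conclusion.** The concern stands as an unstated truncation of the late-toxicity window, paired with an estimator that ignores it. Under even accrual over 24 months, 15 of 30 patients cannot reach 24 months and about 17% of planned late patient-time is lost. Both figures rest on an accrual pattern that the plan does not give. Across the shapes tried, the ranges are about 29% to 75% of patients and 9% to 28% of late time. Deaths, withdrawals and any loss of toxicity review on moving to survival-only follow-up would add to this.

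The consequence is that the crude proportion may understate long-term toxicity, and that a reader could not judge by how much. It does not invalidate the trial. A reader might infer that late toxicity would at least be complete to 12 months for everyone. The documents do not support that either, because patients can leave for survival-only follow-up before then. The point should be corrected because it touches the primary endpoint and the remedy is cheap.

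**What to change.** **Minimum change.**

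- In footnote 2, 10.8.1 and 10.8.2, state that SABR-toxicity review runs to 24 months after SABR or trial closure, whichever is first. Align 10.1.14 and footnote 17 with this.
- Say whether the review continues in patients who move to survival-only follow-up.
- In 11.2.3, report late SABR toxicity separately from acute toxicity. Give the number of patients actually under toxicity review at 12, 18 and 24 months. Beside the crude proportion, show a follow-up-aware estimate, such as cumulative incidence with death as a competing event.
- Do not describe late toxicity as complete to 12 or 24 months unless those numbers support it.

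The cost is a few wording changes, a little more analysis and a more guarded late-safety statement. It adds no visits and does not delay the final analysis.

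**Optional, if the full 2-year window is wanted.** Exempt SABR-toxicity review from the closure rule, run collection to about month 48, and plan a late-toxicity addendum. This costs up to 12 more months of follow-up for the later entrants. It is light only if a reduced visit is written, since the listed follow-up visit also carries examination, vital signs, performance status and pain score, with 3-monthly imaging alongside.

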3 TRIAL SUMMARY

Title	Stereotactic R adiotherapy and A nti- P D1 antibody (P embrolizumab) for O ligometastatic R enal T umours
Abbreviated Title	RAPPOR
Trial Phase	Phase 1b/II
Clinical Indication	Patients with oligometastatic renal cancer (1-5 metastases) considered safe for stereotactic ablative body radiosurgery (SABR)
Trial Type	Prospective, single arm study
Route of administration	SABR treatment (18Gy-20Gy/1#) followed by 200mg pembrolizumab (MK-3475) IV once every 3 weeks for a total of 8 cycles (~6 months).
Trial Blinding	Open label
Number of trial subjects	30 evaluable* patients in total.
Estimated enrolment period	24 months
Estimated duration of trial	36 months
Duration of Participation	~20 months

* Evaluable patients are defined as participants who complete at least one SABR treatment and receive at least one dose of study drug (18-20Gy/1# to at least one lesion with at least one dose of pembrolizumab).

